Appendix 3. IMWG MINIMAL RESIDUAL DISEASE (MRD) Criteria

Assess for MRD (at least by centrally collected flow cytometry and sequencing) for all bone marrow aspirates obtained while a patient is in suspected or actual CR. Confirmation with two consecutive assessments is not required.

| Response | IMWG Criteria |
|-------------------------------------|--|
| Sustained MRD-negative ¹ | MRD negativity in the marrow (NGS) and by imaging as defined below, confirmed minimum of 1 year apart. Subsequent evaluations can be used to further specify the duration of negativity (eg, MRD-negative at 5 years). |
| Flow MRD-negative ² | Absence of phenotypically aberrant clonal plasma cells by NGF† on bone marrow aspirates using the EuroFlow standard operation procedure for MRD detection in multiple myeloma (or validated equivalent method) with a minimum sensitivity of 1 in 10 ⁵ nucleated cells or higher. |
| Sequencing MRD-negative | Absence of clonal plasma cells by NGS on bone marrow aspirate in which presence of a clone is defined as less than two identical sequencing reads obtained after DNA sequencing of bone marrow aspirates using the LymphoSIGHT platform (or validated equivalent method) with a minimum sensitivity of 1 in 10 ⁵ nucleated cells or higher. |
| Imaging-positive MRD-negative | MRD negativity as defined by NGS plus disappearance of every area of increased tracer uptake found at baseline or a preceding PET/CT or decrease to less mediastinal blood pool SUV or decrease to less than that of surrounding normal tissue. |

CT = computed tomography; IMWG=International Myeloma Working Group; MRD = minimal residual disease; NGF = next-generation flow cytometry; NGS = next generation sequencing; positron emission tomography = PET; SUV = standardized uptake value.

Footnotes

1. Sustained MRD negativity, when reported, should also annotate the method used (eg, sustained sequencing MRD- negative).
2. Bone marrow multiparametric flow cytometry MFC should follow NGF guidelines. The reference NGF method is an eight-color two-tube approach, which has been extensively validated. The two-tube approach improves reliability, consistency, and sensitivity because of the acquisition of a greater number of cells. The complete eight-color method should use a lyophilized mixture of antibodies. 5 million cells should be assessed. The method employed should have a sensitivity of detection of at least 1 in 10⁵ plasma cells.

PF-06863135
C1071001
Final Protocol Amendment 9, 28 March 2023

Appendix 4. ECOG PERFORMANCE STATUS

| Grade | ECOG Performance Status |
|-------|--|
| 0 | Fully active, able to carry on all pre-disease performance without restriction. |
| 1 | Restricted in physically strenuous activity but ambulatory and able to carry out work of a light or sedentary nature, eg, light house work, office work. |
| 2 | Ambulatory and capable of all self-care but unable to carry out any work activities. Up and about more than 50% of waking hours. |
| 3 | Capable of only limited self-care, confined to bed or chair more than 50% of waking hours. |
| 4 | Completely disabled. Cannot carry on any self-care. Totally confined to bed or chair. |
| 5 | Dead. |

*As published in Am J Clin Oncol 5:649-655, 1982.⁵³

PF-06863135

C1071001

Final Protocol Amendment 9, 28 March 2023

Appendix 5. CRS AND ICANS MITIGATION AND MANAGEMENT

CRS is a non-antigen-specific cytokine-associated toxicity that occurs as a result of high-level immune activation. CRS is a potentially life-threatening toxicity that has been observed following administration of immune-base therapies for cancer (antibodies and adoptive T-cell therapies). CRS is likely to be a common toxicity that can be managed through supportive care and anti-cytokine interventions.

In cases of suspected cytokine release syndrome, a serum sample should be provided for cytokine release assay analysis by the local lab (see [Section 7.1.3](#)) so as long as the sampling does not interfere with the medical treatment of the patient.

Early intervention should be undertaken at the first sign of CRS; signs may include pyrexia, tachycardia, tachypnea and/or hypotension and are temporally related to PF-06863135 in the absence of alternative etiologies.

The original CRS grading system proposed by Lee et al in 2014² (Table 13) should be used only for the purposes of grading of CRS on the adverse event case report form (CRF), but not for management of CRS. Grading by the more recent ASTCT CRS criteria³ ([Table 15](#)) will be captured along with the Lee et al 2014 criteria on the CRS CRF, and management guidelines will follow ASTCT CRS grading. These treatment guidelines³⁹ may be modified as needed by the responsible Investigator according to the best practices at their institute.

Table 13. Lee et al 2014 CRS revised grading system²

| Toxicity Grade | Characteristics |
|----------------|---|
| 1 | Symptoms are not life threatening and require symptomatic treatment only, eg, Fever, nausea, fatigue, headache, myalgia, malaise. |
| 2 | Grade 2 hypoxia* [decreased oxygen saturation with activity (eg, pulse oximeter <88%); intermittent supplemental oxygen]; or Hypotension responsive to fluids or low-dose of one vasopressor (Table 14) or Grade 2 organ toxicity. |
| 3 | Grade 3 hypoxia* [decreased oxygen saturation at rest (eg, pulse oximeter <88% or partial pressure of oxygen (PaO ₂) <=55 mm Hg)]; or Hypotension requiring high-dose vasopressors or multiple vasopressors (Table 14); or Grade 3 organ toxicity (except transaminitis); or Grade 4 transaminitis. |
| 4 | Life-threatening symptoms; Grade 3 hypoxia* [decreased oxygen saturation at rest (eg, pulse oximeter <88% or partial pressure of oxygen (PaO ₂) <=55 mm Hg)] or Grade 4 organ toxicity (excluding transaminitis). |
| 5 | Death. |

*Modification to the Lee et al CRS Revised Grading System according to the CTCAE v4.03. Transient decreases in oxygen levels below 88% will not be considered to have met the criteria.

PF-06863135

C1071001

Final Protocol Amendment 9, 28 March 2023

The definitions for high-dose vasopressors are shown in Table 14.

Table 14. Definition of High Dose Vasopressor

| Pressor | High Dose (doses less than these would be considered low) |
|--|---|
| Norepinephrine monotherapy | $\geq 20 \mu\text{g}/\text{min}$ |
| Dopamine monotherapy | $\geq 10 \mu\text{g}/\text{kg}/\text{min}$ |
| Phenylephrine monotherapy | $\geq 200 \mu\text{g}/\text{min}$ |
| Epinephrine monotherapy | $\geq 10 \mu\text{g}/\text{min}$ |
| If on vasopressin | Vasopressin + norepinephrine equivalent of $\geq 10 \mu\text{g}/\text{min}^*$ |
| If on combination vasopressors (not vasopressin) | Norepinephrine equivalent of $\geq 20 \mu\text{g}/\text{min}^*$ |

* VASST Trial vasopressor equivalent equation: norepinephrine equivalent dose = [norepinephrine ($\mu\text{g}/\text{min}$)]

+ [dopamine ($\mu\text{g}/\text{kg}/\text{min}$) $\div 2$] + [epinephrine ($\mu\text{g}/\text{min}$)] + [phenylephrine ($\mu\text{g}/\text{min}$) $\div 10$]

Table 15. ASTCT CRS revised grading system³

| CRS parameter: | Fever* | With Hypotension | And/or [†] Hypoxia |
|----------------|-------------------------------|---|--|
| Grade 1 | Temp. $\geq 38^\circ\text{C}$ | None | None |
| Grade 2 | Temp. $\geq 38^\circ\text{C}$ | Not requiring vasopressors | Requiring low-flow [‡] nasal cannula, low-flow [‡] facemask or blow-by |
| Grade 3 | Temp. $\geq 38^\circ\text{C}$ | Requiring a vasopressor with or without vasopressin | Requiring high-flow [‡] nasal cannula, high-flow [‡] facemask, nonrebreather mask, or Venturi mask |
| Grade 4 | Temp. $\geq 38^\circ\text{C}$ | Requiring multiple vasopressors (excluding vasopressin) | Requiring positive pressure (eg, CPAP, BiPAP, intubation and mechanical ventilation) |

Organ toxicities associated with CRS should still be graded according to CTCAE v4.03 and do not influence CRS grading.

* Fever is defined as temperature $\geq 38^\circ\text{C}$ and not attributable to any other cause. In patients who have CRS then receive antipyretic or anticytokine therapy such as tocilizumab or steroids, fever is no longer required to grade subsequent CRS severity. In this case, CRS grading is driven by hypotension and/or hypoxia.

† CRS grade is determined by the more severe event: hypotension or hypoxia not attributable to any other cause. For example, a patient with temperature of 39.5°C hypotension requiring 1 vasopressor, and hypoxia requiring low-flow nasal cannula is classified as grade 3 CRS.

‡ Low-flow nasal cannula or facemask is defined as oxygen delivered at $\leq 6 \text{ L}/\text{min}$. Low flow also includes blow-by oxygen delivery, sometimes used in pediatrics. High-flow nasal cannula or facemask is defined as oxygen delivered at $> 6 \text{ L}/\text{min}$. This is modified from original ASTCT criteria to differentiate between low-flow and high-flow facemask.

PF-06863135

C1071001

Final Protocol Amendment 9, 28 March 2023

CRS management guidelines^{38,39}**ASTCT Grade 1 CRS:**

- Monitor vital signs for worsening of condition.

Fever

- Acetaminophen/paracetamol and hypothermia blanket for the treatment of fever.
- Non-steroidal anti-inflammatory drugs (NSAIDs) such as ibuprofen can be used as second treatment option for fever if not contraindicated.
- Assess for infection using blood and urine cultures, and chest radiography.
- Empiric broad-spectrum antibiotics and filgrastim if neutropenic.
- Maintenance IV fluids for hydration.
- Symptomatic management of constitutional symptoms or organ toxicity.
- Consider tocilizumab 8 mg/kg* IV or siltuximab 11 mg/kg IV for persistent (lasting >3 days) and refractory fever.

ASTCT Grade 2 CRS:

- Monitor vital signs every 4 hours for worsening of condition.

Fever

- Manage as in Grade 1 CRS.

Hypotension

- IV fluid bolus of 500-1000 ml of normal saline. Can give second IV fluid bolus if systolic blood pressure remains <90 mmHg.
- Consider tocilizumab 8 mg/kg (maximum dose 800 mg) IV or siltuximab 11 mg/kg IV for treatment of hypotension refractory to fluid boluses; tocilizumab can be repeated after 6 h if needed.
- If hypotension persists after 2 fluid boluses and anti-IL-6 therapy, start vasopressors, consider transfer to intensive care unit (ICU), obtain echocardiogram (ECHO), and initiate other methods of hemodynamic monitoring.

PF-06863135

C1071001

Final Protocol Amendment 9, 28 March 2023

- In patients at high-risk (bulky disease, older age or comorbidities) or if hypotension persists after 1-2 doses of anti-IL-6 therapy, dexamethasone can be used at 10 mg IV every 6 hrs.

Hypoxia

- Supplemental oxygen.

Tocilizumab or siltuximab \pm corticosteroids and supportive care, as indicated for hypotension.

ASTCT Grade 3 CRS:

- Monitor patient (including continuous ECG monitoring) in an ICU and obtain ECHO if not done already.

Fever

- Manage as in Grade 1 CRS.

Hypotension

- IV boluses, as needed, as recommended for Grade 2 CRS.
- Tocilizumab and siltuximab as recommended for Grade 2 CRS if not administered previously.
- Vasopressors as needed.
- Dexamethasone 10 mg IV every 6 hrs; if refractory, increase to 20 mg IV every 6 hrs.

Hypoxia

- Supplemental oxygen including high-flow oxygen delivery.
- Tocilizumab or siltuximab plus corticosteroids and supportive care, as described above.

ASTCT Grade 4 CRS:

- Monitor patient (including continuous ECG monitoring) in an ICU and obtain ECHO if not done already.

Fever

- Manage as in Grade 1 CRS.

PF-06863135

C1071001

Final Protocol Amendment 9, 28 March 2023

Hypotension

- IV boluses, anti-IL-6 therapy, vasopressors, and hemodynamic monitoring as recommended for grade 3 CRS.
- Methylprednisolone 1 g/day IV.

Hypoxia

- Supplemental oxygen via positive pressure/mechanical ventilation.
- Tocilizumab or siltuximab plus corticosteroids and supportive care, as described above.

Immune effector cell-associated neurotoxicity syndrome (ICANS)

Although less commonly seen than CRS, ICANS has been observed with some T-cell directed therapies and may manifest as delirium, encephalopathy, aphasia, lethargy, difficulty concentrating, agitation, tremor, seizures, and cerebral edema.³ If ICANS is observed in relation to PF-06863135, the ASTCT criteria³ should be followed for its grading and management.^{38,39} These treatment guidelines may be modified as needed by the responsible Investigator according to the best practices at their institute.

Table 16. Immune Effector Cell-Associated Encephalopathy (ICE) Score

| Category | Task | Points |
|--------------------|--|--------|
| Orientation | Orientation to year, month, city, hospital | 4 |
| Naming | Ability to name 3 objects | 3 |
| Following commands | Ability to follow simple commands | 1 |
| Writing | Ability to write a standard sentence | 1 |
| Attention | Ability to count backwards from 100 by 10 | 1 |

PF-06863135

C1071001

Final Protocol Amendment 9, 28 March 2023

Table 17. ASTCT ICANS Grading

| Neurotoxicity Domain | Grade 1 | Grade 2 | Grade 3 | Grade 4 |
|--|-----------------------|------------------|---|--|
| ICE score* | 7-9 | 3-6 | 0-2 | 0 (unarousable and unable to perform ICE) |
| Depressed level of consciousness† | Awakens spontaneously | Awakens to voice | Awakens only to tactile stimulus | Unarousable or requires vigorous or repetitive tactile stimuli to arouse. Stupor or coma |
| Seizure | N/A | N/A | Any clinical seizure that resolves rapidly or non-convulsive seizures on EEG that resolve with intervention | Life-threatening prolonged seizure (>5 min); or repetitive clinical or electrical seizures without return to baseline in between |
| Motor findings‡ | N/A | N/A | N/A | Deep focal motor weakness such as hemiparesis or paraparesis |
| Elevated ICP/cerebral edema | N/A | N/A | Focal/local edema on neuroimaging** | Diffuse cerebral edema on neuroimaging; decerebrate or decorticate posturing; or cranial nerve VI (abducens nerve) palsy; or papilledema; or Cushing's triad |

ICANS grade is determined by the most severe event (ICE score, level of consciousness, seizure, motor findings, raised intracranial pressure[ICP]/cerebral edema) not attributable to any other cause; for example, a patient with an ICE score of 3 who has a generalized seizure is classified as grade 3 ICANS.

* A patient with an ICE score of 0 may be classified as grade 3 ICANS if awake with global aphasia, but a patient with an ICE score of 0 may be classified as grade 4 ICANS if unarousable.

† Depressed level of consciousness should be attributable to no other cause (eg, no sedating medication).

‡ Tremors and myoclonus associated with immune effector cell therapies may be graded according to CTCAE v4.03, but they do not influence ICANS grading.

¶ Intracranial hemorrhage with or without associated edema is not considered a neurotoxicity feature and is excluded from ICANS grading. It may be graded according to CTCAE v4.03.

PF-06863135
C1071001
Final Protocol Amendment 9, 28 March 2023

ICANS Management guidelines^{38,39}

ASTCT ICANS Grade 1:

- Vigilant supportive care; aspiration precautions; intravenous (IV) hydration.
- Withhold oral intake of food, medicines, and fluids, and assess swallowing.
- Convert all oral medications and/or nutrition to IV if swallowing is impaired.
- Avoid medications that cause central nervous system depression.
- Neurology consultation.
- Evaluate elevated intracranial pressure (ICP), if suspected, with fundoscopic exam for papilledema and lumbar puncture for cerebrospinal fluid opening pressure.
- Magnetic resonance imaging (MRI)MRI of the brain with and without contrast; CT scan of the brain can be performed if MRI of the brain is not feasible.
- Daily 30 min electroencephalogram (EEG) until toxicity symptoms resolve; if no seizures are detected on EEG, continue levetiracetam 750 mg every 12 hrs.
- Consider anti-IL-6 therapy with tocilizumab 8 mg/kg (maximum 800 mg) IV or siltuximab 11 mg/kg IV, if there is concurrent CRS.

ASTCT ICANS Grade 2:

- Supportive care and neurological work-up as described for grade 1 ICANS.
- Anti-IL-6 therapy if associated with concurrent CRS, as described for grade 1 ICANS and if not administered previously.
- Dexamethasone 10 mg IV every 6 h or methylprednisolone 1 mg/kg IV every 12 h if refractory to anti-IL-6 therapy, or for ICANS without concurrent CRS.
- Consider transferring patient to intensive-care unit (ICU) if ICANS associated with grade ≥ 2 CRS.

ASTCT ICANS Grade 3:

- Supportive care and neurological work-up as indicated for grade 1 ICANS.
- ICU transfer is recommended.

PF-06863135

C1071001

Final Protocol Amendment 9, 28 March 2023

- If EEG shows non-convulsive status epilepticus:
 - Assess airway, breathing, and circulation; check blood glucose.
 - Lorazepam 0.5 mg intravenously (IV), with additional 0.5 mg IV every 5 min, as needed, up to a total of 2 mg to control electrographical seizures.
 - Levetiracetam 500 mg IV bolus, as well as maintenance doses.
 - If seizures persist, transfer to intensive-care unit (ICU) and treat with phenobarbital loading dose of 60 mg IV.
 - Maintenance doses after resolution of non-convulsive status epilepticus are as follows: lorazepam 0.5 mg IV every 8 h for three doses; levetiracetam 1,000 mg IV every 12 hr; phenobarbital 30 mg IV every 12 hr.
 - Lacosamide may also be considered for treatment of seizures should the seizures persist but should not be used in patients with concurrent CRS in order to avoid arrhythmias and hypotension.
- For convulsive status epilepticus:
 - Convulsive status epilepticus.
 - Assess airway, breathing, and circulation; check blood glucose.
 - Transfer to ICU.
 - Lorazepam 2 mg IV, with additional 2 mg IV to a total of 4 mg to control seizures.
 - Levetiracetam 500 mg IV bolus, as well as maintenance doses.
 - If seizures persist, add phenobarbital treatment at a loading dose of 15 mg/kg IV.
 - Maintenance doses after resolution of convulsive status epilepticus are: lorazepam 0.5 mg IV every 8 h for three doses; levetiracetam 1,000 mg IV every 12 h; phenobarbital 1–3 mg/kg IV every 12 h.
 - Lacosamide may also be considered for treatment of seizures should the seizures persist but should not be used in patients with concurrent CRS in order to avoid arrhythmias and hypotension.
 - Continuous electroencephalogram monitoring should be performed, if seizures are refractory to treatment.

PF-06863135

C1071001

Final Protocol Amendment 9, 28 March 2023

- High-dose methylprednisolone IV 1 g/day for focal/local edema.
- Anti-IL-6 therapy if associated with concurrent CRS, as described for grade 1 ICANS and if not administered previously.
- Corticosteroids as outlined for grade 2 ICANS if symptoms worsen despite anti-IL-6 therapy, or for ICANS without concurrent CRS; continue corticosteroids until improvement to grade 1 ICANS and then taper.

ASTCT ICANS Grade 4:

- Supportive care and neurological work-up as outlined for grade 1 ICANS.
- ICU monitoring; consider mechanical ventilation for airway protection.
- Anti-IL-6 therapy and repeat neuroimaging as described for grade 3 ICANS.
- High-dose methylprednisolone IV 1 g/day continued until improvement to grade 1 ICANS and then taper; for example, methylprednisolone IV 1 g/day for 3 days, followed by rapid taper at 250 mg every 12 h for 2 days, 125 mg every 12 h for 2 days, and 60 mg every 12 h for 2 days.
- For seizures, treat as described for grade 3 ICANS.
- MRI of the spine should be obtained for focal motor weakness.
- To manage elevated ICP:
 - Elevate head end of the patient's bed to an angle of 30 degrees.
 - Hyperventilation to achieve target partial pressure of arterial carbon dioxide (PaCO₂) of 28–30 mmHg, but maintained for no longer than 24 hrs to lower.
 - Hyperosmolar therapy with either mannitol (20 g/dl solution) or hypertonic saline (3% or 23.4%, as detailed below):
 - Mannitol: initial dose 0.5–1 g/kg; maintenance at 0.25–1 g/kg every 6 hrs while monitoring metabolic profile and serum osmolality every 6 hrs, and withhold mannitol if serum osmolality is \geq 320 mOsm/kg, or the osmolality gap is \geq 40.
 - Hypertonic saline: initial 250 ml of 3% hypertonic saline; maintenance at 50–75 ml/h while monitoring electrolytes every 4 hrs, and withhold infusion if serum Na levels reach \geq 155 mEq/l.
 - For patients with imminent herniation: initial 30 ml of 23.4% hypertonic saline; repeat after 15 min, if needed.

PF-06863135

C1071001

Final Protocol Amendment 9, 28 March 2023

- Consider neurosurgery consultation for ventriculoperitoneal shunt in patients with cerebral edema and IV anesthetics for burst-suppression pattern on EEG.
- Metabolic profiling every 6 h and daily CT scan of head, with adjustments in usage of the aforementioned medications to prevent rebound cerebral oedema, renal failure, electrolyte abnormalities, hypovolemia, and hypotension.

090177e19d0be7ca\Approved\Approved On: 29-Mar-2023 19:51 (GMT)

PF-06863135

C1071001

Final Protocol Amendment 9, 28 March 2023

**Appendix 6. INTERNATIONAL MYELOMA WORKING GROUP (IMWG)
MULTIPLE MYELOMA DIAGNOSIS CRITERIA⁴⁵**

Clonal bone marrow plasma cells $\geq 10\%$ or biopsy-proven bony or extramedullary plasmacytoma and any one or more of the following myeloma defining events:

1. Evidence of end organ damage that can be attributed to the underlying plasma cell proliferative disorder, specifically:
 - a. Hypercalcemia: serum calcium >0.25 mmol/L (>1 mg/dL) higher than the upper limit of normal or >2.75 mmol/L (>11 mg/dL).
 - b. Renal insufficiency: creatinine clearance <40 mL per min[†] or serum creatinine >177 μ mol/L (>2 mg/dL).
 - c. Anemia: hemoglobin value of >20 g/L below the lower limit of normal, or a hemoglobin value <100 g/L.
 - d. Bone lesions: one or more osteolytic lesions on skeletal radiography, CT, or PET-CT.[‡]
2. Any one or more of the following biomarkers of malignancy:
 - e. Clonal bone marrow plasma cell percentage^{*} $\geq 60\%$.
 - f. Involved: uninvolved serum free light chain ratio[§] ≥ 100 >1 focal lesions on MRI studies.

PET-CT=¹⁸F-fluorodeoxyglucose PET with CT.

* Clonality should be established by showing κ/λ -light-chain restriction on flow cytometry, immunohistochemistry, or immunofluorescence. Bone marrow plasma cell percentage should preferably be estimated from a core biopsy specimen; in case of a disparity between the aspirate and core biopsy, the highest value should be used.

† Measured or estimated by validated equations.

‡ If bone marrow has less than 10% clonal plasma cells, more than one bone lesion is required to distinguish from solitary plasmacytoma with minimal marrow involvement.

§ These values are based on the serum freelite assay (The Binding Site Group, Birmingham, UK). The involved free light chain must be ≥ 100 mg/L. Each focal lesion must be 5 mm or more in size.

Relapse is defined as progression of disease after an initial response to previous treatment, more than six months after cessation of treatment.

Refractory is defined as resistance to treatment due to lack of response or progression of disease during treatment or within six months after cessation of treatment.

PF-06863135

C1071001

Final Protocol Amendment 9, 28 March 2023

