this case grade 4 thrombocytopenia needs to be accompanied by \geq Grade 2 bleeding to be a DLT). For subjects who experience a platelet count $<10,000/\text{mm}^3$, this is considered a DLT irrespective of other factors with the exception of lenalidomide-related Grade 4 thrombocytopenia manageable by platelet transfusions and lenalidomide dose reduction in the next cycle.

- Grade 3 thrombocytopenia with \geq Grade 2 bleeding.

Non-hematological:

- Grade 4 Adverse Events (AEs).
- Grade 3 AE lasting ≥ 5 days despite optimal supportive care, with the exception of AE attributed to a CRS event (ie, Grade 3 transaminitis).
- Grade 3 CRS, except those CRS that have i) not been maximally treated (ie, lack of administration of standard of care treatment per the institution's, Investigator's, or treating physician's guidelines for the management of CRS) or ii) improved to \leq Grade 1 within 48 hours.
- Grade 4 CRS.
- Confirmed drug-induced liver injury (DILI) meeting Hy's law criteria outlined in [Section 8.4.1](#).
- Grade 4 laboratory abnormalities deemed clinically significant by the investigator shall be reported as Grade 4 AE as described in [Section 8.2.2](#).
- Clinically important or persistent toxicities (eg, toxicities responsible for significant dose delay) that are not included in the above criteria may also be considered a DLT following review by the investigators and the Sponsor. All DLTs need to represent a clinically significant shift from baseline.

The following AEs will not be adjudicated as DLTs:

- Isolated Grade 3 laboratory abnormalities that are not associated with clinical sequelae and are corrected with supplementation/appropriate management within 72 hours of their onset or deemed clinically insignificant by the investigator.

PF-06863135
C1071001
Final Protocol Amendment 9, 28 March 2023

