8.3. Severity Assessment

| GRADE | Clinical Description of Severity |
|-------|--|
| 0 | No change from normal or reference range (This grade is not included in the Version 4.03 CTCAE document but may be used in certain circumstances.) |
| 1 | MILD adverse event |
| 2 | MODERATE adverse event |
| 3 | SEVERE adverse event |
| 4 | LIFE-THREATENING consequences; urgent intervention indicated |
| 5 | DEATH RELATED TO adverse event |

Note the distinction between the severity and the seriousness of an AE. A severe event is not necessarily an SAE. For example, a headache may be severe (interferes significantly with the patient's usual function) but would not be classified as serious unless it met one of the criteria for SAEs, listed above.

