Appendix 4. Cytokine Release Symptoms Revised Grading System

Table 7: Lee et al 2014 CRS revised grading system

Toxicity Grade	Characteristics
1	Symptoms are not life threatening and require symptomatic treatment only, eg, Fever, nausea, fatigue, headache, myalgia, malaise
2	Symptoms require and respond to moderate intervention Oxygen requirement <40% or Hypotension responsive to fluids or low-dose of one vasopressor or Grade 2 organ toxicity
3	Symptoms require and respond to aggressive intervention Oxygen requirement ≥40% or Hypotension requiring high-dose vasopressors or multiple vasopressors or Grade 3 organ toxicity (except transaminitis) or Grade 4 transaminitis
4	Life-threatening symptoms Requirement for ventilator support or Grade 4 organ toxicity (excluding transaminitis)
5	Death

The original CRS grading system proposed by Lee et al in 2014² (Table 13) should be used only for the purposes of grading of CRS on the adverse event case report form (CRF), but not for management of CRS. Grading by the more recent ASTCT CRS criteria³ (Table 15) will be captured along with the Lee et al 2014 criteria on the CRS CRF, and management guidelines will follow ASTCT CRS grading. These treatment guidelines may be modified as needed by the responsible Investigator according to the best practices at their institute.

CRS parameter	Fever	With Hypotension	And/or Hypoxia
Grade 1	Temp. ≥38° C	None	None
Grade 2	Temp. ≥38° C	Not requiring vasopressors	Requiring low-flow nasal cannula, low-flow facemask or blow-by
Grade 3	Temp. ≥38° C	Requiring a vasopressor with or without vasopressin	Requiring high-flow nasal cannula, high-flow facemask, nonrebreather mask, or Venturi mask

Grade 4	Temp. $\geq 38^{\circ}$ C	Requiring multiple vasopressors (excluding vasopressin)	Requiring positive pressure (eg, CPAP, BiPAP, intubation and mechanical ventilation)
---------	---------------------------	---	--

Detailed grading criteria is provided in Appendix 5 of the protocol.

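### Protocol Table 13 gives Grade 3 and Grade 4 CRS the same resting-hypoxia threshold, and the SAP 8.2.4 formula for adverse event duration has its dates reversed, so a d-day event returns 2 − d

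*Protocol*

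**What the plan says.** **CRS grading.** In Protocol Appendix 5, Table 13 (the 2014 scale as modified for this trial), the Grade 3 row lists "Grade 3 hypoxia* [decreased oxygen saturation at rest (eg, pulse oximeter <88" per cent, or PaO2 at most 55 mm Hg. The Grade 4 row reads "Life-threatening symptoms; Grade 3 hypoxia* [decreased oxygen saturation at rest (eg, pulse oximeter <88" per cent, with the same PaO2 limit. The table footnote adds "Transient decreases in oxygen levels below 88% will not be considered to have met the criteria" and applies to both rows.

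SAP Appendix 4 prints a different version of the 2014 scale. Its Grade 3 row begins "Symptoms require and respond to aggressive intervention Oxygen requirement ≥40" per cent, and its Grade 4 row reads "Life-threatening symptoms Requirement for ventilator support or Grade 4 organ toxicity (excluding transaminitis". It then refers the reader to Protocol Appendix 5 for the detailed criteria.

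**Use of the grade.** Protocol Section 3.2 counts as DLTs "Grade 3 CRS, except those CRS that have i) not been maximally treated" or that have improved to at most "Grade 1 within 48 hours". Grade 4 CRS is listed as a DLT with no exception.

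**Duration.** SAP 8.2.4 says that duration may be presented for events of interest such as CRS and ICANS, and defines it as start date minus stop date plus 1. The same section commits to summarizing and listing ICANS duration.

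**The concern.** A grading table should place each event in one grade. For resting hypoxia, Table 13 does so only if the Grade 4 lead-in acts as a condition on the hypoxia text. Appendix 5 does not say that it does, and does not define the lead-in. Take sustained resting hypoxia without life-threatening symptoms that resolves within 48 hours. If the lead-in is a condition, this is a Grade 3 event exempt from the DLT count. If it is not, this is a Grade 4 DLT. Confirmed Grade 4 CRS is also one of the triggers for a priming dose in Protocol Section 3.1.1.3.

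The duration formula subtracts the dates in the wrong order. The duration of CRS matters here: Protocol Section 3.4 gives shorter CRS as the reason for adopting the priming dose.

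**Working it through.** **1. Hypoxia criteria side by side**

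| Source | Grade 3 | Grade 4 |
|---|---|---|
| Protocol Table 13 | Resting SpO2 below 88% or PaO2 ≤55 mm Hg | The same threshold, still labelled Grade 3 hypoxia, after a lead-in on life-threatening symptoms |
| SAP Appendix 4 | Oxygen requirement ≥40% | Ventilator support |

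The two bracketed thresholds in Table 13 match exactly. The rows differ elsewhere: organ toxicity rises from Grade 3 to Grade 4, and hypotension and Grade 4 transaminitis appear only under Grade 3. The overlap is therefore confined to hypoxia. The criteria within the Grade 3 row are joined by an explicit *or*; the Grade 4 lead-in ends in a semicolon with no connective. Protocol Section 8.3 describes Grade 4 events in general as "LIFE-THREATENING consequences; urgent intervention indicated", but nothing links that to Table 13, and the Schedule of Activities footnotes grade CRS by Appendix 5 instead of CTCAE.

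**2. What one reclassified event could do**

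Protocol Table 4 maps DLT counts to decisions. A move from an exempt Grade 3 to a Grade 4 adds one DLT:

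- n = 3, from 0 to 1 DLT: escalate becomes stay.
- n = 6, from 2 to 3 DLTs: stay becomes de-escalate.

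Recomputing the mTPI rule from Protocol Section 9.2.1 (Beta(0.5, 0.5) prior, target 0.25, interval 0.20 to 0.30, exclusion threshold 0.95) gives the same decisions as Table 4 at the sizes checked (n = 2, 3, 4 and 6). This shows what the ambiguity could do; no such case is documented.

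**3. The duration formula**

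For an event that lasts d calendar days, stop = start + d − 1. Then:

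- SAP formula: start − stop + 1 = 2 − d.
- Error: d − (2 − d) = 2d − 2 days.

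| True duration d | SAP formula | Error | Stop − start + 1 |
|---|---|---|---|
| 1 | 1 | 0 | 1 |
| 2 | 0 | 2 | 2 |
| 4 | −2 | 6 | 4 |
| 9 | −7 | 16 | 9 |

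The 9-day and 4-day rows are CRS events described in Protocol Section 3.4. Only a one-day event comes out right. A mean or median of m days prints as 2 − m, so the ranking of cohorts reverses and the longest event appears as the minimum.

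The other SAP intervals run later date minus earlier date plus 1: time to onset in the same section, OS (8.2.2.2), DoR (8.2.2.6), DoCR (8.2.2.7), DoSD (8.2.2.10) and treatment duration (8.2.2.12).

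**4. How many CRS durations could be misstated**

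Protocol Section 1.2.3.1 reports CRS in 87.8% of 41 full-dose monotherapy patients: 36/41 = 0.878. Assume the 41 are the 6 patients at 1000 µg/kg in Section 3.4, the 20 in Part 1.1 and the 15 in Part 2A (6 + 20 + 15 = 41). The documents then give a duration above one day for 2 of the 36 (the 9-day events). The number misstated lies between 2 (2/36 = 5.6%) and 36. The documents give no durations that would narrow this range.

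**The case against.** The strongest reply on Table 13 is that only one reading gives both rows effect. If the lead-in does not qualify the hypoxia text, every Grade 3 hypoxia case is also Grade 4 and the Grade 3 criterion is empty. The protocol also glosses life-threatening elsewhere (Sections 8.2.3 and 8.3), and the table footnote names CTCAE as the source of the modification. The SAP, for its part, defers to Protocol Appendix 5. The first argument is fair, but it infers a rule that the table does not state, and neither general gloss is tied to Table 13. The SAP's pointer leads back to the same overlapping rows.

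The reach is also limited, and this stands. Under SAP 8.2.4, the 2014 grades feed summary tables for the IV cohorts only (23 of 101 patients) and listings for all cohorts; SC summary tables use ASTCT grades. CRS management follows ASTCT grading. Section 3.4 reports only Grade 1 and 2 CRS in escalation.

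On duration, the reply is that this is an obvious transposition that any check of the tables would catch, that the sponsor already quotes positive durations, and that CRS duration is only optional. All true. But ICANS duration is a firm output, and SAP Section 2 says that deviations from the plan will be described in the study report. The clean remedy is to correct the text, not to program something different from it.

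**Conclusion.** Both defects hold as written. Table 13 does not separate Grade 3 from Grade 4 CRS on resting hypoxia except through a lead-in whose role is unstated, and SAP Appendix 4 prints different oxygen criteria for the 2014 scale. The grade decides whether the 48-hour DLT exemption can apply. No dose decision is shown to have been affected, and no recorded case is known to fall in the overlap. However, Section 3.4 describes its data as preliminary, and Section 1.2.3.1 gives CRS frequency without grades, so the documents do not rule out Grade 3 or 4 cases in later cohorts.

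The duration formula is wrong for every event longer than one day, by 2d − 2 days. If CRS duration is presented for the full-dose group, between 2 and 36 of 36 patients with CRS would be misstated, assuming the 6 + 20 + 15 composition above.

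This should be corrected before reporting. It does not call past escalation into question.

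**What to change.** - **Protocol Table 13 and SAP Appendix 4:** reconcile the Grade 3 and Grade 4 rows with each other and across the two documents, and state how the life-threatening lead-in applies. Which clinical criterion to use is for the sponsor to settle. Then check any recorded Grade 3 or 4 CRS against the reconciled text.
- **SAP 8.2.4:** change the duration formula to stop date minus start date plus 1.
- **Minor, Protocol Section 3.2:** add one sentence naming the recorded CRS grade that decides a DLT. The section cites both scales, although Section 8.1.4.2, Appendix 5 and the Schedule of Activities footnotes point to the 2014 grade on the adverse event form.
- **Minor, SAP 8.2.4:** limit the general statement that ASTCT is the primary grading to the SC and IV split given there and in SAP 6.2.

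The cost is text edits in the protocol and SAP and a check of any Grade 3 or 4 CRS cases. No new data are needed.
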